10. STATISTICAL CONSIDERATIONS

10.1. Statistical Analytical Plan

A Statistical Analysis Plan (SAP) describing the details of all safety, efficacy and exploratory analyses will be written and finalized prior to database lock.

10.2. Analysis Populations

The analysis populations are defined as follows:

- Intent-to-Treat (ITT) Population: All subjects who are randomized to study drug. If a subject is less than 75% compliant with dosing of study drug, the subject will be included in the ‘ITT’ analyses, but not in the ‘Per Protocol’ analyses for efficacy endpoints.
- Safety Population: All subjects who receive at least one dose of study drug.
- Per-protocol (PP) Population: All randomized subjects who complete the study drug dosing through POD14 and do not have any major protocol deviations.

10.3. Statistical Methods

10.3.1. General Approach

All analysis variables will be summarized descriptively by each dosing regimen, active and matching vehicle placebo groups, respectively, within each study part. Summary statistics for continuous measures will be defined as mean, standard deviation, 95% confidence interval, median, and range. Categorical measures will be summarized by the number and percent of subjects.

Inferential statistics for primary and secondary efficacy endpoints will include Student t-test (with normality assumption met) or Wilcoxon rank-sum test (with normality unmet) for continuous endpoints, and Chi-square test for categorical endpoints.

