10.3.2. Analysis of Efficacy

The primary analysis populations will be the ‘Intent-to-Treat’ Population. A subset of efficacy analyses will be examined for the Per-protocol Population as supportive analysis.

The primary efficacy analyses will include, for each dosing regimen, active and placebo separately, the summary statistics of:

- 1) ACC on POD15;
- 2) Pain grade on POD15;

- 3) Change from baseline (POD1/pre-dose) of ACC at POD15;
- 4) Change from baseline (POD1/pre-dose) of pain grade at POD15

Secondary efficacy analyses will include for each dosing regimen, active and placebo separately:

- 1) the summary statistics of:

- ACC on PODs 4, 8, 22/EOT (Part A) or PODs 4, 8 (Part B);
- Change from baseline (POD1/pre-dose) of ACC on PODs 4, 8, 22/EOT (Part A) or on PODs 4, 8 (Part B);
- ACC grade* at PODs 4, 8, 15, 22/EOT (Part A) or PODs 4, 8 and 15/EOT (Part B);
- Change from baseline (POD1/pre-dose) of ACC grade at PODs 4, 8, 15, 22/EOT (Part A) or PODs 4, 8 and 15/EOT (Part B);
- Anterior chamber flare grade at PODs 4, 8, 15, 22/EOT (Part A) or PODs 4, 8 and 15/EOT (Part B);
- Change from baseline (POD1/pre-dose) of anterior chamber flare at PODs 4, 8, 15, 22/EOT (Part A) or PODs 4, 8 and 15/EOT (Part B);
- Pain grade for each treatment at PODs 4, 8, 22/EOT (Part A) or PODs 4, 8 (Part B);
- Change from baseline (POD1/pre-dose) of pain grade at PODs 4, 8, 15, 22/EOT (Part A) or PODs 4, 8 and 15/EOT (Part B);
- Visual acuity (ETDRS Best corrected Visual Acuity measurement – pinhole method) at PODs 4, 8, 15, 22/EOT (Part A) or PODs 4, 8 and 15/EOT (Part B);
- Change from baseline (POD1/pre-dose) of visual acuity at PODs 4, 8, 15, 22/EOT (Part A) or PODs 4, 8 and 15/EOT (Part B)

* Anterior Chamber Cell Grade Definition:

Grade 0	Grade 1	Grade 2	Grade 3	Grade 4
0 cell	1-5 cells	6-15 cells	16-30 cells	> 30 cells

- 2) the proportion of subjects

- with ACC = 0 at PODs 4, 8, 15 and 22/EOT (Part A) or PODs 4, 8 and 15/EOT (Part B) without receiving rescue medication;

- who are pain-free at PODs 4, 8, 15 and 22/EOT (Part A) or PODs 4, 8 and 15/EOT (Part B) without receiving rescue medication;
- with AC flare grade = 0 at PODs 4, 8, 15 and 22/EOT (Part A) or PODs 4, 8 and 15/EOT (Part B) without receiving rescue medication.

Details of statistical analyses will be included in the SAP.

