5.1.1. General Statistical Analyses

All analyses will be done by each study part separately.

All analysis variables will be summarized descriptively by each active dosing regimen and its matching vehicle placebo group.

Continuous measures will be summarized as mean and standard deviation. In most cases, 95% confidence interval, median, and range will also be provided. Inferential statistics for continuous primary and secondary efficacy endpoints will include Student t-test and/or Mann-Whitney test.

Categorical measures will be summarized by counts. Due to the small sample size, the percentage of subjects will be provided only when it is necessary. The total number for the relevant population and the number of subjects who are still on study drug will be listed with the counts of categorical measures. “On study drug” will be defined in Section 5.1.6.2.

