The proportion of subjects with ACC count = 0, pain-free, or ACF grade = 0 without receiving rescue medication will be calculated for each active dosing regimen and its matching vehicle placebo for each visit during POD1 – POD22 (Part A) and POD1 – POD15 (Part B) in [Table 14.2.4](#) and [Figure 14.2.4](#). The denominator will be the total number of subjects randomized in each treatment group. LOCF will be used to impute missing values and all assessments after subjects stopped being on study drug.

All subjects' inflammation and pain information will be presented in [Listing 16.2.6.2](#) and best correct visual acuity information will be presented in [Listing 16.2.6.3](#).

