6.6. Changes to Protocol-Planned Analyses

- Added analyses for ACC grade at PODs 4, 8, 15 (and 22 for Part A).

	Document Number: CLN.001.SAP	Version: 0
	Document Title: Clinical Study CPN-201 Statistical Analysis Plan	Page 28 of 35

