16	“LOCF will not be used for “complete” subjects even if they have stopped study drug earlier than POD21 (Part A) and POD14 (Part B).”	Removed from SAP.	The change reflects the intended purpose of the LOCF analysis.
21	For changes from baseline of ACC count, ACC grade, pain grade, ACF grade, and ETDRS acuity (logMAR score), statistical comparison between each active dosing regimen and its matching vehicle	
 1. The comparison was carried out for the means of the efficacy endpoints as well. 2. For efficacy endpoints, the Pearson-Chi-Square test was used to compare the proportions of 	New Exploratory analyses added.

	Document Number: CPN-201.SAP Appendix Document Title: Clinical Study CPN-201 Statistical Analysis Plan Follow-Up	Version: 1 Page: 4 of 5
--	---	--

	
placebo will be carried out for each visit during POD4 - POD22 (Part A) and POD4 – POD15 (Part B) using t-test and Mann-Whitney non-parametric tests.
	
“resolved” subjects (‘Sustained’ Grade = 0) between each active group and its matching placebo group at POD4 and sustained at all later visits.
 
3. IOP means and changes from baseline were compared between active treatment groups and their matching placebo groups.
	
21	
Sensitivity Analyses:
 
“A subset of efficacy analyses will be examined for the per-protocol population as supportive analysis.”
	
These analyses will not be conducted.
	
Only 5 out of 132 (3.8%) subjects were excluded from Per Protocol population because of protocol deviations. The differences from the LOCF analyses of efficacy endpoints will be negligible.

21	
Sensitivity Analyses:
 
“Since only first ACC count will be used to define the proportion of subject with ACC count = 0,
	
These analyses will not be conducted.
	
The analyses will use the first ACC count - this is comparable to real-world clinical practice. Because only 6 (4.5%) subjects had

	Document Number: CPN-201.SAP Appendix Document Title: Clinical Study CPN-201 Statistical Analysis Plan Follow-Up	Version: 1 Page 5 of 5
--	---	---

	
analyses of using second ACC count and/or a combination of the two counts will be explored.”
		
different ACC counts at a visit, the other analyses are redundant.

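### The protocol's chi-square comparison of the responder proportions is missing from the SAP and is not declared as a change, while a supplementary, non-protocol proportion is given a test

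*Protocol*

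**What the plan says.** **Protocol.** Section 10.3.1 (and the synopsis) names the tests for primary and secondary efficacy endpoints: Student t-test or Wilcoxon rank-sum "for continuous endpoints, and Chi-square test for categorical endpoints". Section 10.3.2 lists three proportions among the secondary analyses, beginning with subjects "with ACC = 0 at PODs 4, 8, 15 and 22/EOT (Part A) or PODs 4, 8 and 15/EOT (Part B) without receiving rescue medication", followed by the same for pain-free and for flare grade 0. The secondary objective in Table 4 is a comparison of active with matching vehicle.

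**SAP.** Section 5.1.1 confines testing to continuous measures: "Inferential statistics for continuous primary and secondary efficacy endpoints will include Student t-test and/or Mann-Whitney test". On the others it says "Categorical measures will be summarized by counts", with percentages only where necessary. Section 5.3.2 calculates "The proportion of subjects with ACC count = 0, pain-free, or ACF grade = 0 without receiving rescue medication" by arm and visit for Table 14.2.4 and Figure 14.2.4, and adds "The denominator will be the total number of subjects randomized in each treatment group". It states no test, difference or interval for these proportions. Section 6.6, the list of changes to protocol-planned analyses, has one entry: "Added analyses for ACC grade at PODs 4, 8, 15 (and 22 for Part A").

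**SAP Appendix.** In section 2 (Modifications), "the Pearson-Chi-Square test was used to compare the proportions of" resolved subjects, active against matching placebo, at POD4 and sustained at all later visits. The entry is marked as a new exploratory analysis. 'Resolved' is defined in SAP 5.3.4.1 as a supplementary analysis. It is not among the protocol's endpoints.

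**The concern.** A between-arm comparison planned in the protocol disappears from the SAP without being declared. It matters for two reasons.

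- **Use of the results.** SAP section 1 gives the study's purpose as choosing a dosage regimen for Phase 3. For that decision, a responder difference with its uncertainty is more useful than two separate percentages from about 21 subjects each. This is a judgement about usefulness. Protocol 3.5.2 speaks of absolute ACC counts informing pivotal trials that will use ACC grading, and does not ask for a responder difference.
- **Consistency.** Under the Appendix, the only proportion with a p-value is one the protocol did not list. A reader of the study report would see a test on sustained resolution from POD4 and none on the listed endpoints beside it, with no explanation.

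**Working it through.** **1. The documents side by side**

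| Item | Protocol | SAP | SAP Appendix |
|---|---|---|---|
| ACC = 0, pain-free, flare = 0 without rescue | Secondary endpoints (10.3.2); chi-square (10.3.1) | Proportion per arm and visit (5.3.2); no contrast stated | No contrast added |
| ACC count, ACC grade, pain grade, flare grade | t-test or rank-sum for continuous endpoints | t-test and Mann-Whitney on change from baseline at each visit (5.3.2) | Comparison of means added |
| 'Resolved' (sustained zero on study drug) | Not listed | Supplementary (5.3.4.1) | Pearson chi-square, POD4 and sustained |
| Declaration of the dropped test | – | Not in 6.6 | Not mentioned |

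The 'resolved' test does not stand in for the missing one. It is worded for POD4 onward and requires zero at every later visit while still on study drug. Even at POD15, resolved status in Part A would also require POD22.

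**2. Number of contrasts**

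- Part A: 3 endpoints × 4 post-dose visits (PODs 4, 8, 15, 22) × 1 regimen = 12.
- Part B: 3 endpoints × 3 visits (PODs 4, 8, 15) × 2 regimens = 18.
- Total: 12 + 18 = 30.

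**3. Sample size**

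The plan enrols 21 per arm for about 20 completers at 5% dropout: 21 × 0.95 = 19.95, which reproduces. The plan states no alpha, power or effect size, so there is nothing further to reproduce.

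**4. Precision of a restored contrast (assumed rates)**

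Protocol 1.4.2 cites about 40% ACC clearing and 60% pain-free after 15 days on a marketed steroid. It gives no placebo rate, so a range is assumed. The half-width of the 95% CI is 1.96 × √[p₁(1−p₁)/21 + p₂(1−p₂)/21].

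- ACC = 0, 40% active: ±0.23 against 5% on placebo, up to ±0.28 against 25%.
- Pain-free, 60% active: ±0.27 against 20% on placebo, up to ±0.30 against 40%.

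The Appendix refers to 132 subjects. If these are equally split over six arms (132/6 = 22), the half-widths are ±0.22 to ±0.29.

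**5. Range of assumed counts at 21 per arm**

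These are not trial data. Newcombe limits, with Wilson limits (l, u) for each arm and difference d = p₁ − p₂, are d − √[(p₁−l₁)² + (u₂−p₂)²] and d + √[(u₁−p₁)² + (p₂−l₂)²].

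For 8/21 versus 4/21: p₁ = 0.381 (0.208, 0.591), p₂ = 0.190 (0.077, 0.400), d = 0.190. The lower limit is 0.190 − √(0.173² + 0.210²) = −0.08. The upper limit is 0.190 + √(0.210² + 0.113²) = 0.43.

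| Active | Vehicle | Difference (points) | Newcombe 95% CI | Pearson p | Fisher p |
|---|---|---|---|---|---|
| 8/21 | 2/21 | 28.6 | 2.6 to 50.7 | 0.030 | 0.067 |
| 8/21 | 4/21 | 19.0 | −8.2 to 43.0 | 0.172 | 0.306 |
| 9/21 | 4/21 | 23.8 | −4.1 to 47.3 | 0.095 | 0.181 |
| 10/21 | 4/21 | 28.6 | 0.1 to 51.6 | 0.0495 | 0.100 |
| 13/21 | 6/21 | 33.3 | 3.3 to 56.1 | 0.030 | 0.062 |
| 13/21 | 8/21 | 23.8 | −5.9 to 48.3 | 0.123 | 0.217 |

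The intervals are 48 to 54 points wide throughout. One responder more or fewer moves the Pearson p-value across 0.05 (9/21 and 10/21 against 4/21), and Pearson and Fisher can fall on opposite sides of it. At this sample size the interval tells more than the p-value.

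**The case against.** The strongest case on the other side is this. The study tests no formal hypotheses and all p-values are descriptive (Protocol 10.5, SAP section 2). The responder proportions are reported for both arms at every visit over all randomized subjects, so anyone can derive the difference and interval. ACC count, ACC grade, pain grade and flare grade are all tested at each visit, and the responder endpoints are the lowest category of those same scales. The wording in SAP 5.1.1 is not exclusive, SAP 5.3.4 allows further exploratory analyses, and the layout of Table 14.2.4 is not visible. The protocol itself asks for a chi-square test, not a risk difference or a Newcombe interval, and thirty more unadjusted p-values have a cost.

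Most of this stands and limits the size of the point. It does not explain why a test named in the protocol is absent from the SAP text and from the list of changes, or why the one proportion test then added is for another measure. The request for an interval goes beyond the protocol and is offered as the better summary at this sample size.

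A reader might go further and infer selective reporting, or that 'resolved' was chosen late to obtain a result. The documents do not support that. The measure is defined in the main SAP and shares Table 14.2.4 with the responder proportions. Only its test comes from the Appendix, where it is already marked exploratory. The Appendix cites observed counts (5 of 132 subjects excluded from the per-protocol population, 6 with differing ACC counts), so some data were in hand, but nothing says treatment codes were open.

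**Conclusion.** The point holds as an undeclared departure of the SAP from the protocol on listed secondary endpoints: a planned contrast is missing for three responder proportions, about 30 comparisons in all, while a supplementary proportion is tested. It is worth correcting, but it does not threaten the primary analysis.

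It would be wrong to read this as POD15 having no treatment comparison, because the primary ACC count and pain grade are compared there. The precision figures (about ±23 to ±30 points at 21 per arm) rest on assumed placebo rates, on active rates borrowed from a marketed product, and on equal arms. The finding about the text does not depend on them.

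**What to change.** - In SAP 5.3.2 and Table 14.2.4, for each of the three responder proportions at each post-dose POD, report the active-minus-vehicle difference with a 95% CI (for example Newcombe) and the protocol's chi-square test. Use Fisher's exact test as a check where counts are sparse: at 40% versus 5%, the expected responders are 21 × (0.40 + 0.05)/2 = 4.7 per arm.
- Label these p-values descriptive and unadjusted, and state that there are about 30.
- Show the 'resolved' comparison in the same format, and state that its test, not the measure, was added in the Appendix.
- If the sponsor prefers not to restore the test, list and justify its removal in SAP 6.6 and in the study report.

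The cost is a few columns in an existing table and more descriptive p-values. No additional data or subjects are needed.

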10.3.2. Analysis of Efficacy

The primary analysis populations will be the ‘Intent-to-Treat’ Population. A subset of efficacy analyses will be examined for the Per-protocol Population as supportive analysis.

The primary efficacy analyses will include, for each dosing regimen, active and placebo separately, the summary statistics of:

- 1) ACC on POD15;
- 2) Pain grade on POD15;

- 3) Change from baseline (POD1/pre-dose) of ACC at POD15;
- 4) Change from baseline (POD1/pre-dose) of pain grade at POD15

Secondary efficacy analyses will include for each dosing regimen, active and placebo separately:

- 1) the summary statistics of:

- ACC on PODs 4, 8, 22/EOT (Part A) or PODs 4, 8 (Part B);
- Change from baseline (POD1/pre-dose) of ACC on PODs 4, 8, 22/EOT (Part A) or on PODs 4, 8 (Part B);
- ACC grade* at PODs 4, 8, 15, 22/EOT (Part A) or PODs 4, 8 and 15/EOT (Part B);
- Change from baseline (POD1/pre-dose) of ACC grade at PODs 4, 8, 15, 22/EOT (Part A) or PODs 4, 8 and 15/EOT (Part B);
- Anterior chamber flare grade at PODs 4, 8, 15, 22/EOT (Part A) or PODs 4, 8 and 15/EOT (Part B);
- Change from baseline (POD1/pre-dose) of anterior chamber flare at PODs 4, 8, 15, 22/EOT (Part A) or PODs 4, 8 and 15/EOT (Part B);
- Pain grade for each treatment at PODs 4, 8, 22/EOT (Part A) or PODs 4, 8 (Part B);
- Change from baseline (POD1/pre-dose) of pain grade at PODs 4, 8, 15, 22/EOT (Part A) or PODs 4, 8 and 15/EOT (Part B);
- Visual acuity (ETDRS Best corrected Visual Acuity measurement – pinhole method) at PODs 4, 8, 15, 22/EOT (Part A) or PODs 4, 8 and 15/EOT (Part B);
- Change from baseline (POD1/pre-dose) of visual acuity at PODs 4, 8, 15, 22/EOT (Part A) or PODs 4, 8 and 15/EOT (Part B)

* Anterior Chamber Cell Grade Definition:

Grade 0	Grade 1	Grade 2	Grade 3	Grade 4
0 cell	1-5 cells	6-15 cells	16-30 cells	> 30 cells

- 2) the proportion of subjects

- with ACC = 0 at PODs 4, 8, 15 and 22/EOT (Part A) or PODs 4, 8 and 15/EOT (Part B) without receiving rescue medication;

- who are pain-free at PODs 4, 8, 15 and 22/EOT (Part A) or PODs 4, 8 and 15/EOT (Part B) without receiving rescue medication;
- with AC flare grade = 0 at PODs 4, 8, 15 and 22/EOT (Part A) or PODs 4, 8 and 15/EOT (Part B) without receiving rescue medication.

Details of statistical analyses will be included in the SAP.

10.3.3. Analysis of Safety

Analysis of safety data will be performed for all subjects in the Safety Population.

Adverse events (AE) will be summarized by total number of any AE, number of subjects reporting the AE, ocular AEs (affecting the study eye and/or the non-study eye and/or both eyes, when appropriate), ocular TEAEs in the study eye, systemic AEs, SAEs, suspected unexpected serious adverse reaction (SUSARs), discontinuing study drug due to an AE, by relationship to study drug and/or ocular surgical procedure, and by severity. Adverse events will be coded using Medical Dictionary for Regulatory Activities (MedDRA, most current version) and categorized by system organ class and preferred terms.

The analyses of IOP will include the summary statistics of IOP and its change from baseline (POD1/pre-dose) at each visit, the proportion of subjects with an IOP ≥ 24 mmHg AND an increase ≥ 10 mm Hg from pre-dose baseline, and the proportion of subjects with an IOP > 30 mmHg at any time following initiation of study drug.

The proportion of subjects with a visual acuity worsening from POD1/pre-dose visit of ≥ 2 lines will also be summarized.

Ocular symptoms, comfort grading assessment, ophthalmoscopy findings, and slit lamp biomicroscopy results will be categorically summarized.

Details of statistical analyses will be included in the SAP.

10.3.4. Interim Analysis:

No interim analyses are planned for this study.

10.4. Sample Size Estimation

This is a Phase 2a trial to explore dosing regimens, and no formal sample size calculations were used to determine the number of subjects to be enrolled into the trial. The sample size of 21 subjects in each study treatment group was selected based on feasibility and integrated analysis of literature data. Assuming a dropout rate of 5%, approximately 21 subjects will be

enrolled into each treatment arm so that approximately 20 subjects per treatment arm would be expected to complete study drug dosing through the POD15 visit.

10.5. Level of Significance

All reported p-values will be considered descriptive and hypothesis generating.

10.6. Procedure for Accounting for Missing, Unused, or Spurious Data

For the ACC endpoint, the last observation prior to the first rescue medication will be carried forward for data summary at the subsequent time points (visits) for the subjects who received rescue medication during the study. Other missing data will be imputed according to the SAP.

10.7. Procedure for Reporting Deviations from the Statistical Plan

Any deviations from the SAP will be described and a justification given in the final clinical study report.

10.8. Subjects to be Included in the Analysis

Efficacy analysis will be performed for the ITT population. A subset of the efficacy analysis will be repeated using data from the 'Per Protocol' population.

AEs and other safety parameters will be analyzed for all randomized subjects receiving at least 1 dose of randomized study drug (Safety Population).

11. SUPPORTING DOCUMENTATION AND OPERATIONAL CONSIDERATIONS

11.1. Regulatory, Ethical and Legal Obligations

11.1.1. Declaration of Helsinki

The Principal Investigator will ensure that this study is conducted in accordance with the most recent revision of the Declaration of Helsinki.

11.1.2. Good Clinical Practice

The Study will be conducted according to the study protocol and to Standard Operating Procedures (SOPs) that meet the guidelines provided by the International Conference on Harmonisation (ICH) for Good Clinical Practice in clinical studies and applicable regulatory requirements.

11.1.3. Institutional Review Boards/Ethics Committees

This protocol and the informed consent form must be approved by an appropriately constituted and qualified IRB and the approvals made available to the Sponsor or designee prior to the start of enrollment into the study. Materials used to recruit subjects or supplied to subjects for the study will be approved by the appropriate IRB and the approvals made available to the Sponsor or designee prior to their use. In addition, the APP13007 Investigator's Brochure will be submitted to the IRB. Written IRB approval must adequately identify the protocol and informed consent form. Copies of all approved materials, all correspondence with the IRB, and written approval from the IRB must be made available to the Sponsor (or designated Study Monitor).

Any modification of study procedures or amendments to the protocol must be approved by the IRB and submitted to FDA prior to implementation. In the event that a modification or amendment is considered by the Investigator to be immediately necessary to ensure subject safety, the Investigator will promptly notify his or her IRB, the Study Medical Monitor, and the CRO for Study Management and Monitoring who will then notify the Sponsor.

Investigators will report all SAEs reported at their site to their IRB, as appropriate.

